### **5.7.3            Study Termination**

The study may be terminated at any time by the Sponsor if serious side effects occur, if potential risks to study participants are identified, if the Investigator does not adhere to the protocol, or if, in the Sponsor's judgment, there are no further benefits to be achieved from the study. In the event

that the clinical development of the study vaccine is discontinued, the Sponsor shall inform all Investigators/institutions and regulatory authorities.

CONFIDENTIAL

## 6 TREATMENT OF SUBJECTS

### 6.1 Identity of Study Vaccines

The TAP-COVID-19 vaccine is comprised of a purified recombinant SARS-CoV-2 RBD-Fc conjugated to a TMV NtK carrier. The TAP-COVID-19 vaccine will be combined with CpG 7909 adjuvant prior to administration.

The product will be formulated and shipped as multi-dose vials. The vaccine doses will be diluted as appropriate by the site pharmacist to 15 µg or 45 µg doses of antigen along with 0.5 mg CpG adjuvant to be delivered in a single 0.5 mL IM injection. A detailed description for vaccine preparation is provided in the pharmacy manual.

Buffered saline solution (with thimerosal) will be used as placebo.

A description of the study vaccines is presented in Table 6-1.

**Table 6-1 Study Vaccines**

Study Vaccine	Dosage Form (Volume, Route)	TAP-COVID-19 Dose	Manufacturer
TAP-COVID-19 + CpG (0.5 mg)	Injectable solution, (0.5 mL, intramuscular injection)	15 µg	Kentucky BioProcessing, Inc.
TAP-COVID-19 + CpG (0.5 mg)	Injectable solution, (0.5 mL, intramuscular injection)	45 µg	Kentucky BioProcessing, Inc.
Placebo (buffered saline solution)	Injectable solution, (0.5 mL, intramuscular injection)	Not applicable	Kentucky BioProcessing, Inc.

TAP-COVID-19, CpG adjuvant, and the placebo (buffered saline solution) will be sourced by KBP.

### 6.2 Treatments Administered

Both Part A (18-49 years) and Part B (50-85 years) will be randomized in a 2:1 ratio (active:placebo) for each treatment dose (15 µg and 45 µg TAP-COVID-19 vaccine + 0.5 mg CpG) for a total of 90 subjects per Part (30 subjects 15 µg TAP-COVID-19 vaccine + 0.5 mg CpG:30 subjects 45 µg TAP-COVID-19 vaccine + 0.5 mg CpG:30 subjects placebo).

Treatment A: TAP-COVID-19 vaccine (15 µg) + CpG (0.5 mg) IM injection on Day 1 and Day 22 ( $\pm 3$  days)

Treatment B: TAP-COVID-19 vaccine (45 µg) + CpG (0.5 mg) IM injection on Day 1 and Day 22 ( $\pm 3$  days)

Treatment C: Placebo (buffered saline solution) IM injection on Day 1 and Day 22 ( $\pm 3$  days)

The IM dose for Part C Expansion (optional) will be determined after reviewing the safety and immunogenicity data through Day 43 from Parts A and B (low and high dose).

### **6.3        Method of Assigning Subjects to Treatment Groups**

ICON will prepare the randomization scheme in accordance with its SOPs and the randomization plan, which reflect GCP standards. Refer to [Section 9.3](#) for a description of randomization methods. Eligible subjects will be assigned to a treatment group according to the list of subject randomization assignments.

### **6.4        Measurements of Treatment Compliance**

All study vaccine doses will be prepared and administered by delegated and trained staff at the clinical site(s). Details regarding dosing, including the dose administered and the date and time of dosing, will be recorded.

### **6.5        Study Vaccine Storage, Accountability, and Retention**

#### **6.5.1        Storage Conditions**

The Investigator will ensure that all the study vaccines are stored per the instructions accompanying the study vaccine. In addition, the Investigator will ensure that study vaccines are handled in accordance with the FDA regulations concerning the storage and administration of investigational products.

Refer to the SRM for additional study vaccine storage instructions.

#### **6.5.2        Drug Accountability and Retention**

The Investigator must ensure that all study vaccine supplies are kept in a secure locked area with access limited to those authorized by the Investigator. The Investigator must maintain accurate records of the receipt of all study vaccine shipped by KBP or their representative, including but not limited to the date received, lot number, expiration date, amount received, and the disposition of all study vaccine. Current dispensing records will also be maintained including the date and amount of study vaccine dispensed and the subject receiving the drug. All remaining study vaccine not required by regulations to be held by the clinical site(s) must be returned to KBP or their representative immediately after the study is completed.

### **6.6        Packaging and Labeling**

#### **6.6.1        Study Vaccine**

Study vaccine will be supplied as a concentrated injectable solution packaged in 10-mL multi-dose vials with preservative (thimerosal). CpG sterile solution will be supplied as a concentrated solution with preservative (thimerosal). Placebo will be buffered saline solution with preservative (thimerosal) provided by KBP.

## **6.6.2            Blinding of Treatment Assignment**

ICON will maintain the randomization code in a secure location with controls to prevent unauthorized access, including the computer program written to generate the randomization, randomization codes, program log, seed number used by the program, copy of the randomization plan along with approval documentation as appropriate, and the write-protected electronic storage medium.

The site and CRO will name an unblinded statistician to provide the randomization code. The pharmacists will be unblinded. Since the placebo and vaccine will not be identical in appearance, the staff member administering the doses will be unblinded and will not participate in any additional study activities. In order to preserve the blind, study vaccine will be prepared and administered in a manner that masks the content for both the subject and any observers. Investigators, site staff, subjects, CRO [except for the unblinded team members preparing the data for unblinded iSRC review] will remain blinded until the completion of the study. The Sponsor will remain blinded to individual subjects' treatment assignment from the beginning of the study through Day 43. When the data is unblinded for the interim analysis after all subjects complete Day 43, the Sponsor will be unblinded.

## **6.6.3            Unblinding of Treatment Assignment**

### **6.6.3.1        Unblinding for Adverse Event/Safety Reasons**

Should an SAE or other circumstance require that the blind be broken to ensure subject safety, the Investigator must immediately notify the medical monitor and/or Sponsor. ICON/designee will notify the Sponsor as soon as possible and will release the treatment assignment of the subject to the appropriate personnel in accordance with the applicable SSP.

If the treatment assignment is unblinded by the site pharmacist or any party other than ICON, the Investigator must notify ICON in writing and document the course of events in the source records. Any subject for whom the treatment code is prematurely released will be withdrawn from the study.

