- For Parts A and B, a positive urine drug screen without evidence of corresponding prescribed concomitant medication(s) at Screening is exclusionary. A positive drug screen result with a corresponding prescribed concomitant medication will be allowed if, in the opinion of the Investigator and Medical Monitor, the concomitant medication does not make the subject unsuitable to participate in the clinical trial.
- Not performed for Part C.
- Serial nasopharyngeal swabs (RT-PCR) will be performed on subjects that report either potential exposure to SARS-CoV-2 (ie, close contact tests positive for SARS-CoV-2) or symptoms of SARS-CoV-2 infection. Testing will occur every 2 weeks for a total of 4 weeks (if 2 consecutive negative tests) or until negative after a positive result. Positive results will be reported as an AESI ([Section 8.2.2](#)) and subjects followed for disease severity, duration, and outcome.

CONFIDENTIAL

- i. Review of Diary Card ([Appendix A](#)) will include a check that the Diary Card has been completed appropriately and re-training the subjects, if necessary. Any illogical entries will be queried by the site and corrected if appropriate.
- j. During telephone visits, CRU staff will interview the subjects about any potential exposure to the virus. If a subject has had potential exposure, the CRU will ask the subject to come in for an unscheduled visit which will include a nasopharyngeal swab. Subjects will be reminded to contact the clinical site any time there is potential exposure to SARS-CoV-2.
- k. Subjects will be monitored for SARS-CoV-2 exposure for potential asymptomatic infection throughout the study. CRU staff will interview subjects about any potential exposure to the virus. If a subject has had potential exposure, the CRU will perform an unscheduled nasopharyngeal swab.
- l. Adverse events include questioning regarding the specifically elicited events on the Diary Card and complaints spontaneously reported in response to nondirective questions.
- m. SAEs, MAAEs, NOCDs, and AESIs will be collected from Day 1 through Day 365/approximately 1 year after first vaccination.
- n. Includes all medications taken during the first 43 days of the study, including those started 30 days before and ongoing at vaccination.

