### **3.2.2 Secondary Endpoints**

Safety:

- Unsolicited AEs, MAAEs, and AESIs up to Day 43
- SAEs, MAAEs, NOCDs, and AESIs up to Day 365 (approximately 1 year after first vaccination)

Immunogenicity:

- Vaccine ELISA of both RBD IgG and IgM antibodies and neutralizing antibody titers for each treatment group:
  - GMT at baseline and Days 15, 22, 43, 90, 181, 273, and 365
  - GMT ratio ( $GMT_{placebo}/GMT_{TAP-COVID-19}$ ) at baseline and Days 22, 29, 43, 90, 181, 273, and 365
  - GMFR at Days 8, 22, 29, 43, 90, 181, 273, and 365 relative to baseline
  - Seroconversion rates on Days 8, 15, 22, 29, 43, 90, 181, 273, and 365. Seroconversion is defined as the proportion of subjects at the respective time point that have detectable antibodies (IgG and IgM) against SARS-CoV-2 Spike Protein RBD following challenge with vaccine (and potentially by natural asymptomatic or symptomatic infection by the virus in case of a placebo subject).
  - GMI on Days 8, 22, 29, 43, 90, 181, 273, and 365

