#### **4.1.3                   Definition of Study Completion**

End-of-study procedures will be performed as specified in the Schedule of Assessments and Procedures ([Table 1-1](#)); subjects who withdraw from the study early will have EOS procedures performed at the time of discontinuation. If a subject refuses to return for the EOS blood samples, the safety follow-up will be completed via telephone. Subjects with ongoing clinically significant clinical or laboratory findings will be followed until the finding is resolved or medically stable; reasonable attempts will be made to follow-up with subjects. The subject's participation in the study will end once all study assessments and follow-up have been completed.

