## **5.5 Individual Discontinuation Criteria**

The occurrence of the following findings in an individual subject may result in discontinuation from the study vaccine. Subjects will be asked to participate in the scheduled Follow-up Visits, including at a minimum Day 365, to check safety and immunogenicity.

- Subjects experiences an SAE assessed as possibly related, probably related, or related to study vaccine without a plausible alternative explanation.
- Subject has generalized urticaria during the 7-day post vaccination period.
- Subject develops a Grade 4 local reaction for which there is no alternative plausible explanation.
- Subject experiences laryngospasm, bronchospasm, or anaphylaxis after vaccine administration considered related to the vaccine.
- Subject develops a fever  $>40^{\circ}\text{C}/104^{\circ}\text{F}$  during the 7 days post vaccination period that is assessed as possibly related, probably related, or related to study vaccine without a plausible alternative explanation.
- Single Grade 3 AEs or AESIs that are possibly, probably, or definitely related to study vaccine without a plausible alternative explanation.
- Subject experiences any Grade 3 or higher abnormality in the same laboratory parameter determined by the Investigator or medical monitor as clinically significant and that are assessed as possibly related, probably related, or related to study vaccine without a plausible alternative explanation.

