## **5.6 Subject Withdrawal**

Subjects are free to withdraw from the study at any time, for any reason, and without prejudice to further treatment. The Investigator may withdraw a subject if, in the Investigator's judgment, continued participation would pose unacceptable risk to the subject or to the integrity of the study data. All procedures for early withdrawal must be completed. Reasons for withdrawal may include:

- AE
- SAE that is possibly related, probably related, or related, without a plausible alternative explanation
- Lost to follow-up
- Physician decision
- Pregnancy
- Protocol deviation
- Study terminated by Sponsor
- Withdrawal by subject
- Death
- Other

Subjects who are withdrawn for reasons other than AEs may be replaced.

In the event of a subject's withdrawal from study vaccine, the Investigator will promptly notify the Sponsor and will make every effort to complete the EOS assessments, unless the subject withdraws consent. All withdrawn subjects with ongoing clinically significant clinical or laboratory findings will be followed until the finding is resolved or medically stable; reasonable attempts will be made to follow-up with subjects. The subject will also be asked to participate in a Follow-up Visit at approximately Day 365 to check safety and immunogenicity.

Subjects may be withdrawn from receiving the second dose of the study vaccine if they meet specific Study Halting Rules (see [Section 5.7.2](#)) or Individual Discontinuation Criteria ([Section 5.5](#)). If a subject is withdrawn due to meeting a Study Halting Rule or Individual Discontinuation Criteria, they will be asked to participate in the scheduled Follow-up Visits, including at a minimum Day 365, to check safety and immunogenicity.

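### Section 6.6.3.1 withdraws a subject from the study after premature release of the treatment code, without saying that safety follow-up to Day 365 continues

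*Combined protocol and SAP*

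**What the plan says.** Section 6.6.3.1 has two paragraphs. The first covers the authorised route and opens "Should an SAE or other circumstance require that the blind be broken to ensure subject safety". The code is then released through ICON or a designee, and withdrawal is not mentioned. The second opens "If the treatment assignment is unblinded by the site pharmacist or any party other than ICON", requires written notification and documentation, and ends: "Any subject for whom the treatment code is prematurely released will be withdrawn from the study".

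The protocol plans one year of safety collection. A footnote to Table 1-1 says "SAEs, MAAEs, NOCDs, and AESIs will be collected from Day 1 through Day 365/approximately 1 year after first vaccination", and Section 3.2.2 makes these events a secondary endpoint to Day 365.

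Other sections deal with follow-up after a subject stops early:

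- Section 4.1.3: "subjects who withdraw from the study early will have EOS procedures performed at the time of discontinuation".
- Section 5.5, for subjects who meet an individual discontinuation criterion: "Subjects will be asked to participate in the scheduled Follow-up Visits, including at a minimum Day 365, to check safety and immunogenicity".
- Section 5.6, for withdrawal from study vaccine: "The subject will also be asked to participate in a Follow-up Visit at approximately Day 365 to check safety and immunogenicity". Its last paragraph goes further. Subjects withdrawn under a halting rule or a discontinuation criterion are asked to attend the scheduled visits, with Day 365 as the minimum.
- Section 5.7.2: subjects withdrawn from study vaccine go on being monitored.
- Section 8.3: subjects withdrawn from the study for an AE may be followed to its outcome and are asked back at about Day 365.
- Section 8.4: every SAE and AESI is followed until it resolves.

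None of these names withdrawal caused by code release.

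**The concern.** The rule in 6.6.3.1 is mandatory and ends participation in the study, not only vaccination. Sections 5.5 and 5.7.2 refer to the study vaccine when only dosing stops, so the difference in wording cannot be set aside as loose drafting.

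This is a first-in-human trial whose objectives are largely about safety. If a subject is unblinded because of a serious event and is then withdrawn, follow-up stops for a reason connected with the outcome, so the missing data would be informative. If the rule covers only irregular releases, the missing data need not be informative, but the trial still stops collecting data on a dosed subject for an administrative reason.

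What is at stake is the detection of new MAAEs, NOCDs, AESIs and SAEs after the release. Classification may also be affected. Section 8 defines an NOCD partly by its not being resolved at the end-of-study assessment, and Section 4.1.3 brings that assessment forward to the time of discontinuation.

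**Working it through.** There is no planned figure to reproduce. The protocol states no sample size calculation, and the point does not depend on one. The check is a comparison of clauses and a count of visits.

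**Step 1: reach of the sentence.** Two readings are open.

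- Narrow: the sentence belongs to its own paragraph and covers only release by someone other than ICON.
- Wide: it speaks of any subject, stands under the heading for safety unblinding, and leaves prematurely undefined. Section 6.6.2 keeps investigators and site staff blinded until the study is complete, so any earlier release to them could be called premature.

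The text does not settle which is meant.

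**Step 2: which follow-up clause applies.** A subject with a vaccine-related SAE can meet a Section 5.5 criterion and also be unblinded. Section 5.5 then asks for the scheduled visits, while 6.6.3.1, on the wide reading, withdraws the subject from the study. No section says which prevails. On the narrow reading, a subject whose code leaked without any AE has even less cover. Section 5.5, the last paragraph of 5.6, and 8.3 all depend on an AE, a discontinuation criterion or a halting rule.

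**Step 3: the count.** Table 1-1 schedules these contacts after Day 43: Days 76, 90, 120, 150, 181, 273 and 365, which is 7. Days 76, 120 and 150 are telephone visits. For a subject withdrawn by Day 43:

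| Clause taken to apply | Contacts kept | Contacts lost |
|---|---|---|
| 6.6.3.1 with only the end-of-study procedures of 4.1.3 | 0 | 7 − 0 = 7 |
| Day 365 request in 5.6 (vaccine withdrawal) or 8.3 (AE withdrawal) | 1 | 7 − 1 = 6 |
| 5.5 or last paragraph of 5.6 (scheduled visits, at minimum Day 365) | 1 to 7 | 7 − 7 = 0 up to 7 − 1 = 6 |

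Section 5.7.2 gives no number of visits and refers back to 5.6. Section 8.4 schedules no visits; it follows an event that is already known. A release after the Day 181 visit would leave only 2 contacts at stake (Days 273 and 365). A release well before Day 43 would also put earlier visits at risk.

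**Step 4: analysis sets.** Under Section 9.2, anyone who received any study vaccine or placebo is in the Safety Population, and anyone in it with any serology data is in the mITT Population. Withdrawal removes nobody from either set, and events already recorded stay in the analysis.

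**The case against.** The strongest reply is that the sentence is a sanction for irregular unblinding. The authorised route has its own paragraph with no withdrawal in it, and the quoted sentence follows the text on release by other parties. That reading is natural and may be what was intended. It cannot be confirmed, because the key word is undefined. Nor does it explain why a dosed subject should leave the study because someone else released the code.

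A second reply is that follow-up is protected elsewhere. A reader might infer from 6.6.3.1 that subjects unblinded for safety lose their whole year of follow-up. The documents taken together do not support that. The last paragraph of 5.6 asks for scheduled visits after a halting rule or discontinuation criterion, 8.3 asks AE withdrawals back at about Day 365, and 8.4 follows SAEs and AESIs to resolution. This reply stands in part. The protections cover known events and certain reasons for withdrawal. They do not mention code release, and only some of them keep the intermediate visits.

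A third reply is that overlap between 5.5 and 6.6.3.1 may be rare. Meeting a 5.5 criterion does not require individual unblinding, and after a halting rule the unblinded review is done by the iSRC. That also stands, and it limits the expected number of subjects affected.

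**Conclusion.** The point holds as an unresolved rule that puts follow-up at risk. For a subject withdrawn by Day 43 the loss is between 0 and 7 of 7 scheduled contacts, and the width of that range shows how much the text leaves open.

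It would go too far to say that long-term harm will be understated, or to state a share of an arm or a number of days lost. The documents give neither an expected number of code breaks nor a date for them, so such figures would rest on assumptions. It would also go too far to call the subjects lost to analysis, since their place in the Safety and mITT Populations is unaffected. Only events arising after withdrawal, and later immunogenicity samples, are at risk.

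The conclusion assumes that sites would apply the sentence as written. I class it as a cheap improvement.

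**What to change.** Amend the last sentence of 6.6.3.1 so that release of a treatment code does not by itself end study participation. Ask such subjects to complete the scheduled safety and immunogenicity visits through Day 365, in line with Section 5.5. Document the unblinding and flag these subjects in a listing.

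In the same amendment, define premature release, state whether authorised unblinding through ICON is covered, and reconcile the passage with Sections 5.5, 5.6 and 8.3 so that one follow-up clause clearly applies. Any decision about further vaccination stays with the existing sections. The analysis populations need no change.

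The cost is a sentence or two in the protocol and a flag in a listing. The drawback is that some later assessments in these few subjects are made unblinded; the listing lets a reader see which ones.

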### **6.6.3.2        Unblinding for Interim Analyses**

An unblinded interim analysis will be performed on the safety and immunogenicity data collected for each of the 4 dose groups (Part A low dose, Part A high dose, Part B low dose, and Part B high dose). Unblinded interim analysis will occur for the Part A low dose group (including active and placebo subjects) when the first 30 subjects vaccinated have data available from Day 1 through Day 43. The remaining cohorts will have an unblinded interim analysis performed when all subjects in the cohort have data from Day 1 through Day 43. For the interim analysis, treatment codes will be unblinded after the data are deemed ready for the analysis and the data has been monitored. The CRO [except for the unblinded team members preparing the data for unblinded iSRC review], Investigator, and clinical staff will not have access to the unblinded treatment group interim analyses and will remain blinded until completion of the study. The Sponsor will be unblinded at the interim analysis. The iSRC will communicate immunogenicity data to the study

team in a blinded manner so that clinical development decisions for additional studies can be made by the Sponsor.

